**A Mechanistic Perspective on Post-Activation Performance
Enhancement Responsiveness: A Randomized Controlled
Study of Acute Changes in Muscle Architecture, Contractile
Property Kinetics, and Muscle Excitability**

NCT06982937

18.05.2025

Objectives and endpoints.

The primary objective is to test whether a heavy conditioning activity (CA; one set of 2–3 repetitions at ~90% 1RM) produces post-activation performance enhancement (PAPE) in countermovement jump (CMJ) height compared with a control treadmill warm-up within the 4–12 min window after the intervention. The analysis does not assume *a priori* when the maximal effect occurs; instead, the minute of maximal between-group difference (denoted T^*) will be identified empirically. The primary endpoint is the change in CMJ height from baseline (ΔCMJ) at post-intervention time points (4, 6, 8, 10, 12 min). Secondary endpoints include the time-course of ΔCMJ within the experimental group (EXP), individual responder status at each time point, and the associations between neuromuscular phenotype—estimated as %MHC-I from tensiomyography (TMG)—and the magnitude, timing, and likelihood of response. Ultrasound (USG) morphology (muscle thickness, pennation angle, derived fascicle length) will be analysed in parallel to performance endpoints. Electromyography (EMG), where available, will be treated analogously to USG/TMG (see below).

Data handling and derived variables.

At each time point, CMJ height is the mean of three trials; ΔCMJ and percentage change (% ΔCMJ) will be computed relative to baseline. Individual response is classified using MDC. USG outcomes will be averaged across three images; fascicle length is calculated as thickness divided by the sine of pennation angle (degrees converted to radians). TMG-based %MHC-I is estimated from delay, contraction, and half-relaxation times using the published multivariable model; TMG amplitudes and time constants may also be expressed as Δ or % Δ . If EMG is collected, signals will be band-pass filtered, rectified, quantified with 50-ms RMS, normalized (to MVC or M-wave), and summarized over task-relevant phases; % Δ at 4–12 min is computed analogously. Values >3.5 SD from group-time means will be flagged; primary analyses include all data, with winsorized sensitivity checks reported only if inferences change. Missing data will be not imputed for the primary analysis; mixed-effects models accommodate missingness assuming MAR.

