Primary analysis and identification of the peak time (T^*).

The confirmatory analysis uses a RM-ANOVA with ΔCMJ as the outcome, Group (EXP vs CON), Time (time effect: 4, 6, 8, 10, 12 min), and Group \times Time. If the interaction is significant, we estimate adjusted between-group contrasts at each minute with Bonferroni correction across the five time points. T^* is defined as the minute showing the largest positive EXP–CON difference in estimated marginal means (EMMs) with the smallest p-value. We report the EMM difference at T^* (95% CI) and effect size (d’Cohen). Greenhouse–Geisser correction if needed.

Within-group time-course and kinetics.

To describe the temporal profile without prespecifying a target minute, we analyse ΔCMJ across time within EXP using a one-way repeated-measures ANOVA (or LMM if assumptions are violated), followed by Bonferroni-adjusted pairwise EMMs to locate the within-group peak. To characterise response timing at the individual level, we model time to first and time to peak response (4–12 min) using Kaplan–Meier curves with censoring at 12 min, compare strata by log-rank tests, and fit Cox proportional-hazards models to estimate hazard ratios (HR, 95% CI) and concordance (C-index). This kinetics framework provides an assumption-light estimate of when athletes typically express PAPE.

Responder analyses and discrimination.

Responder distributions (Positive/neutral/adverse) will be compared between EXP and CON at each minute using likelihood χ^2 test. For mechanistic discrimination at specific minutes (including T^* once identified), we fit logistic models with %MHC-I as a continuous predictor and report ORs (95% CI),

Nagelkerke R², AIC, Hosmer–Lemeshow calibration, and ROC-AUC with sensitivity, specificity, and Youden's J cut-offs. Moderation analysis also will be used with simple slope analysis.

Phenotype and morphology linkages (USG/TMG/EMG).

Associations between %MHC-I and Δ CMJ will be quantified at each minute using Pearson's r. USG variables (thickness, pennation angle, fascicle length) will be analysed with the same three lenses applied to performance: (i) within-EXP time-course (rmANOVA/LMM with Tukey), (ii) responder linkage at each minute (one-way ANOVA or robust alternative; Hedges' g for P vs X), and (iii) phenotype linkage (correlations and moderation models). TMG (e.g., Dm, Tc, Tr) and EMG (e.g., normalized RMS, median frequency) follow this identical framework to ensure coherence across modalities.

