Moderation and mediation (pre-specified).

All moderators and predictors will be mean-centered; multicollinearity is checked (VIF < 5). Primary moderation models test whether (a) baseline CMJ modifies the effect of %MHC-I on Δ CMJ and (b) baseline morphology (thickness, pennation angle, fascicle length) modifies the effect of baseline CMJ on Δ CMJ. Significant interactions will be decomposed with simple slopes at -1 SD, mean, and +1 SD, with 95% CIs via nonparametric bootstrap (1,000 resamples) and publication-ready interaction plots. Exploratory mediation tests whether acute morphological change (e.g., % Δ thickness at a given minute) transmits baseline morphology effects to % Δ CMJ; indirect, direct, and total effects will be estimated by bootstrap (5,000 resamples; bias-corrected CIs) and interpreted cautiously.

Assumptions, multiplicity, and robustness.

Model diagnostics include residual normality (Shapiro–Wilk), homoscedasticity (residual–fitted patterns, Breusch–Pagan), linearity, and independence by design. Sphericity is tested for rmANOVA (Mauchly) with Greenhouse–Geisser corrections as needed. If mechanistic variables are skewed, appropriate transformations (e.g., log for EMG amplitude) are considered; otherwise we rely on LMM robustness. Multiplicity is controlled via Holm across the five between-group contrasts, FDR for correlation families, and restraint in post-hoc testing; moderation/mediation will be estimation-focused with full interval reporting and are not used to redefine the primary inference.

Reporting, visualization, and software.

We report means \pm SD with 95% CIs; between-group effects as Hedges' g; within-subject effects as d_{nZ} ; ANOVA-style effects as η^2 ; logistic results as ORs with AUC; and survival results as HRs with concordance. Figures include EMM trajectories with 95% CIs, individual waterfall plots with MDC bands, ROC curves for %MHC-I, Kaplan–Meier curves for first/peak response, interaction plots for significant moderations, and path diagrams for supported mediations. Analyses will be performed in Jamovi 2.6 and STATISTICA 13.1.

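### Correlating absolute TMG contraction and half-relaxation times with %MHC-I is largely built in, because %MHC-I is calculated from those times

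*Combined protocol and SAP*

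**What the plan says.** *Objectives and endpoints* defines the neuromuscular phenotype as a TMG-derived quantity, "estimated as %MHC-I from tensiomyography (TMG"). *Data handling and derived variables* names its inputs: "TMG-based %MHC-I is estimated from delay, contraction, and half-relaxation times using the published multivariable model". Amplitude (Dm) is not among them.

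*Phenotype and morphology linkages (USG/TMG/EMG)* sets out three lenses for the ultrasound variables. The third is "iii) phenotype linkage (correlations and moderation models"). The section then extends all three to TMG: "TMG (e.g., Dm, Tc, Tr) and EMG (e.g., normalized RMS, median frequency) follow this identical framework". Nothing exempts Tc or Tr from the third lens or mentions that they overlap with %MHC-I.

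Two further statements affect the size of the problem:

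- **Scale.** *Data handling and derived variables* says "TMG amplitudes and time constants may also be expressed as Δ or % Δ". The scale for the phenotype lens is left open.
- **Multiplicity.** *Assumptions, multiplicity, and robustness* specifies "FDR for correlation families" and does not say which correlations form a family, which procedure is used, or at what level.

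**The concern.** A variable that is an input to an index correlates with that index whether or not there is any biology to find. If absolute Tc or Tr is correlated with %MHC-I, a sizeable r can be published as a link between fibre phenotype and contractile kinetics when it carries no independent evidence of one. Contractile kinetics are in the study title, so readers will look for this result.

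There may be a second effect. A step-up FDR procedure sets the threshold for each test partly by how many other tests in the family are rejected. Built-in rejections pooled with informative correlations (Dm, ultrasound, EMG) would make it easier for chance findings among the latter to pass.

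**Working it through.** The documents give no sample size, model weights, FDR procedure or FDR level, so there is no planned figure to reproduce. What follows shows the size under stated assumptions.

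**From the documents:** %MHC-I is a function of three TMG times; Tc and Tr go through the phenotype lens; there are five "post-intervention time points (4, 6, 8, 10, 12 min").

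**Assumed:** standardised times with equal same-sign weights and common inter-correlation ρ; n = 20; Benjamini-Hochberg at q = 0.05; Tr means half-relaxation time; phenotype linkage means correlation with %MHC-I.

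**1. Absolute value against the index, same occasion.** r = (1+2ρ)/√(3+6ρ) = √((1+2ρ)/3).
- ρ = 0: √(1/3) = 0.58
- ρ = 0.3: √(1.6/3) = 0.73
- ρ = 0.5: √(2/3) = 0.82

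The chance of p < 0.05 at n = 20, from Φ(atanh(r)·√17 − 1.96), is about 77%, 97% and above 99%. With unequal same-sign weights (1:2:1, 1:1:3 and 3:1:1, ρ from 0 to 0.6), r for a single component runs from 0.30 to 0.95.

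**2. Post-intervention absolute value against a baseline index.** With ρ = 0 and no true change, r = reliability × 0.577. Reliability 0.80 gives 0.46 and reliability 0.95 gives 0.55.

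**3. Change score against a baseline index.** Baseline error enters the index, and enters the change with the opposite sign. With no true change and s² = 1 − reliability, r = −s²/(√(2s²)·√(3+6ρ)).
- Reliability 0.8, ρ = 0: −0.2/(0.632 × 1.732) = −0.18
- Reliability 0.9, ρ = 0: −0.1/(0.447 × 1.732) = −0.13
- Reliability 0.9, ρ = 0.5: −0.1/(0.447 × 2.449) = −0.09

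**4. Effect on a shared FDR family.** Take six variables at five minutes, or 30 tests. Tc and Tr supply 10. Dm and the three ultrasound variables supply 20, all taken as truly null.
- The 20 alone: the threshold for the smallest p-value is 0.05/20 = 0.0025, and the chance of any false link is about 5%.
- Limit with all 10 built-in tests rejected and independent tests: the threshold is 11 × 0.05/30 = 0.0183, and 1 − (1 − 0.0183)^20 = 0.31.
- Simulated at n = 20 (6,000 runs per setting), with minutes independent or correlated 0.8 within person:

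| Built-in r | Independent minutes | Correlated minutes |
|---|---|---|
| 0.58 | 20% | 13% |
| 0.73 | 30% | 18% |
| 0.30 | 5% | 4% |
| −0.15 | 3% | 3% |

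Repeat simulations put the low end for r = 0.58 to 0.73 at about 12%, so the range is roughly 12-31%. At r = 0.30, or on the change scale, there is no inflation. In a smaller family of 2 built-in and 6 null tests, the threshold rises from 0.05/6 = 0.0083 to 3 × 0.05/8 = 0.0188, and the chance of a false link from about 5% to 9-12% (n = 20 to 40).

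The FDR of the whole family stays nominally controlled, because the built-in tests count as true discoveries. What weakens is protection for the informative tests.

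**The case against.** The strongest reply concerns scale. For performance, the phenotype lens relates %MHC-I to the change in jump height, and the TMG variables are told to follow the same framework. The title speaks of acute changes, and TMG times may be expressed as change. A change-score reading is therefore at least as natural as an absolute one. On it the built-in r is only about −0.09 to −0.18, which at n = 20 reaches p < 0.05 in about 7-12% of tests. **This stands.** A reader might infer that the plan will report a strong kinetics link whatever the biology. The documents do not support that: the scale is open, and because the weights are not given, opposite-sign weights could shrink even the absolute-value correlation.

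A reader might also take the looser FDR threshold as a fact of the design. It is not. If each variable's five minutes form their own family, the effect on other variables disappears. The 31% is a limiting case with every built-in test rejected and independent tests.

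Third, a reader might infer that a Tc by %MHC-I interaction is planned. *Moderation and mediation (pre-specified)* lists baseline jump height with %MHC-I, and baseline morphology with baseline jump height. No Tc by %MHC-I term appears. The third lens does mention moderation models without saying which apply to TMG, so excluding that pair is a sensible precaution. The VIF < 5 check would not reliably catch it: at r = 0.82 the two-predictor VIF is 1/(1 − 0.667) = 3.0.

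Finally, barring Tc and Tr from the lens altogether would discard a legitimate question: whether change in contraction time after the conditioning activity differs by phenotype. **This also stands**, and the fix allows for it.

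None of this removes the core. Absolute values remain permitted, Tc and Tr are named, and no exemption is written.

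**Conclusion.** The concern holds for absolute values. If the plan is followed with absolute Tc or Tr, the correlation with %MHC-I is largely built in. Its size is about 0.58 to 0.82 under equal same-sign weights with ρ from 0 to 0.5, and somewhat lower (0.46 to 0.55 at ρ = 0) for post-intervention values against a baseline index. For change scores the built-in part is small and negative. The FDR consequence is conditional on family membership: about 5% rising to roughly 12-31% in the assumed 30-test family, and no rise if the families are separate or the built-in r is low.

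These sizes rest on assumed weights, n, reliability, FDR procedure and level, and on the natural reading of Tr and of phenotype linkage. The overlap itself rests on the text alone.

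The primary between-group comparison of jump height does not use these correlations and is unaffected. The stated secondary endpoint links phenotype to the jump response rather than to TMG variables, so it is not circular in this way. The point should be corrected before analysis, but it does not threaten the main inference.

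**What to change.** In *Phenotype and morphology linkages (USG/TMG/EMG)*, third lens:

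- Do not correlate absolute delay time, Tc or Tr with %MHC-I, and do not pair any of them with %MHC-I in a moderation model.
- If change in these times is related to baseline %MHC-I, report it as descriptive, with a note that shared baseline measurement error induces a weak negative correlation.
- Keep Tc and Tr in the first two lenses (time-course and responder linkage), and keep Dm in all three.

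In *Assumptions, multiplicity, and robustness*, state that no variable used to compute %MHC-I enters an FDR family with the other phenotype correlations. Listing the families, with the procedure and level, would make that statement checkable.

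The cost is a few sentences and no change to data collection. The small downside is that absolute Tc and Tr are no longer tested against phenotype.

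### The %MHC-I response analyses and both primary moderation models specify no analysis population and no Group×predictor term, so as written they estimate associations with change rather than with response to the CA

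*Combined protocol and SAP*

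**What the plan says.** *Objectives and endpoints* defines the CA effect by comparison with a control treadmill warm-up. It lists as a secondary endpoint the association of neuromuscular phenotype (%MHC-I) with "the magnitude, timing, and likelihood of response". *Data handling and derived variables* states: "Individual response is classified using MDC". That rule looks at each participant's own change, without reference to the control arm.

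Group is named in two places: the confirmatory RM-ANOVA with its five EXP–CON contrasts, and the responder-distribution test, where categories "will be compared between EXP and CON at each minute". Neither contains %MHC-I.

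The analyses that do contain %MHC-I name no arm:

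- *Responder analyses and discrimination*: "we fit logistic models with %MHC-I as a continuous predictor and report ORs (95% CI", with ROC-AUC and cut-offs. The same paragraph adds "Moderation analysis also will be used with simple slope analysis", with no moderator, predictor or population.
- *Phenotype and morphology linkages*: correlations of %MHC-I with ΔCMJ "will be quantified at each minute using" Pearson's r. Of the three lenses listed for ultrasound, TMG and EMG, only the first is tied to an arm ("i) within-EXP time-course (rmANOVA/LMM with Tukey"). The third, phenotype linkage, is not.
- *Moderation and mediation*: "Primary moderation models test whether (a) baseline CMJ modifies the effect of %MHC-I on" ΔCMJ. Model (b), on baseline morphology and baseline CMJ, is equally silent.

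The Kaplan–Meier and Cox analyses stand under a within-group heading, so EXP-only is natural there, but the log-rank strata and Cox covariates are not named.

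**The concern.** A variable can predict ΔCMJ for reasons unrelated to the CA: general warm-up, repeated jumping, or measurement error. In a randomized controlled study the control arm is what separates these from response to the CA, and the separating quantity is the difference between arms in the slope on the predictor. No model in the plan is specified to estimate it.

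Baseline CMJ is the clearest case because it is a component of ΔCMJ. Measurement error alone gives a negative slope of ΔCMJ on baseline in both arms. This concerns the baseline slope, not the product terms in models (a) and (b).

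At stake is the mechanistic conclusion: an association that is identical in CON could be reported as phenotype-dependent PAPE.

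**Working it through.** The documents give no sample size, expected correlation or reliability for these analyses, so there is no stated figure to reproduce. The check has a reading step and an illustration on assumed inputs.

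**Step 1. The two readings of the unstated population.**

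| Reading | What the slope estimates | Separates CA response from shared change? |
|---|---|---|
| EXP only | Association with change after the CA | No: no control reference |
| Both arms, no Group term | One slope averaged over two treatments | No: arms mixed |
| Both arms, Group×predictor | EXP slope minus CON slope | Yes |

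**Step 2. Correlation of %MHC-I with ΔCMJ at one minute.** Assumed: 20 or 30 per arm, EXP–CON mean difference 0.5 SD, total within-arm SD 1, and the same r in both arms, so there is no true modification of the CA effect. Model: y = 0.5·Group + r·M + √(1−r²)·e, with M and e standard normal; two-sided 0.05; 20,000 runs per setting.

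| Analysis | n=20 per arm, r 0.3–0.5 | n=30 per arm, r 0.3–0.5 |
|---|---|---|
| EXP-only r significant | about 25–65% | 37–83% |
| Pooled r, no Group (secondary reading) | 45–90% | 63–98% |
| Group×%MHC-I significant | about 5% | about 5% |

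Hand check of the EXP-only row by Fisher's z, power ≈ Φ(atanh(r)·√(n−3) − 1.96). At n=20, r=0.3: 0.3095×√17 − 1.96 = −0.68, which gives 25%. At n=30, r=0.5: 0.5493×√27 − 1.96 = 0.89, which gives 81%. With r = 0 in both arms, all three analyses reject in about 5%.

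**Step 3. The plan's FDR over the five minutes.** With the same r in both arms at every minute and an assumed within-subject residual correlation of 0.5 or 0.8 (8,000 runs), at least one minute is significant after Benjamini–Hochberg in EXP in 23–76% (n=20) and 36–92% (n=30), against about 4–5% for Group×%MHC-I. FDR controls chance findings; it does not remove a real association that both arms share.

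**Step 4. Baseline CMJ with no true change in either arm.** If reliability is R, the expected correlation of baseline with change is −(1−R)/√(2(1−R)) = −√((1−R)/2). At assumed R of 0.95, 0.90 and 0.80 this is −√0.025 = −0.16, −√0.05 = −0.22 and −√0.10 = −0.32. At n=20 per arm the EXP-only correlation is significant in 10%, 16% and 27% of 4,000 runs, and the pooled one in 17%, 28% and 51%. Group×baseline CMJ stays at 4–5%.

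**Step 5. Moderation models.** These figures use a different scale (residual SD 1, product effect 0.3–0.5 equal in both arms) and are not comparable with Step 2. The EXP-only product term is significant in 18–40% (n=20) and 28–61% (n=30), against about 5% for the three-way term with Group.

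**Step 6. Price of the interaction.** With r 0.3–0.5 in EXP and 0 in CON, Group×%MHC-I has power of about 15–35% (n=20) and 20–50% (n=30). Check at n=20, difference 0.5: SE ≈ √(2/20) = 0.316; 0.5/0.316 − 1.96 = −0.38, which gives 35%. At r 0.4–0.5 the 95% CI half-width is 0.64–0.66 SD per SD at n=20 and 0.51–0.52 at n=30. The three-way term has about 10–22% and 16–35% power when its product effect exists in EXP only.

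**The case against.** The plan calls this endpoint associations and defines response by each participant's own change. It also says that moderation and mediation are estimation-focused and do not redefine the primary inference. A within-EXP association is legitimate if labelled as such. The within-EXP lens, the within-group heading over the survival analyses and the talk of mechanistic discrimination all point to EXP-only, so the larger pooled figures belong to the less natural reading. Nothing in the documents shows that %MHC-I correlates 0.3–0.5 with ΔCMJ after a treadmill warm-up, and no rationale is given for a shared product effect. The interaction proposed instead is weak at plausible sizes.

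Most of this stands and limits the point. It does not remove it. The estimation-focused statement covers moderation and mediation, not the correlations or logistic/ROC models. EXP-only is not written for these models and would not supply a control reference. The greater power of an EXP-only correlation is for a different question.

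A reader might infer that the plan makes it impossible to separate response to the CA from shared change, or that its main result is compromised. The documents support neither. The gap is in the models as written: CON has ΔCMJ at the same minutes, so the comparison can be made, and the RM-ANOVA with its contrasts does not depend on these analyses. Nor may one infer that the unspecified moderation sentence excludes Group as a moderator; it simply does not prespecify it.

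**Conclusion.** The point holds for secondary and mechanistic conclusions. Pearson's r, the logistic/ROC models, the phenotype-linkage lens and moderation models (a) and (b) specify neither a population nor a Group×predictor term, and neither available reading isolates response to the CA.

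The harm is conditional on an association shared by both arms. For %MHC-I its size rests entirely on the assumed correlations and sample sizes above. For baseline CMJ the mechanism is structural, and only its size depends on the assumed reliability. This is a cheap improvement that should be made, at the lower end of that priority.

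**What to change.** 1. State the analysis population for each model.
2. For ΔCMJ at each minute, fit both arms with Group, %MHC-I and Group×%MHC-I, and likewise Group×baseline CMJ. Report the EXP-minus-CON slope difference with its 95% CI, using the plan's FDR over the five minutes, as the basis for any claim about responsiveness to the CA. Keep Pearson's r by arm as descriptive.
3. For moderation (a) and (b), either add the three-way terms (Group×%MHC-I×baseline CMJ; Group×baseline CMJ×morphology) with all lower-order terms before any CA-specific claim, or label the models as within-arm descriptive associations. Two-way Group terms alone would leave the common product term in place.
4. Name the Cox covariates and log-rank strata, and label the within-EXP odds ratio, AUC and hazard ratio descriptive. A Group interaction is not worth requiring for the responder models. If 2.5–10% of CON were positive by MDC (assumed), the exact binomial gives at most one CON responder in 39–91% of trials at n=20 and 18–83% at n=30; for example, 0.9²⁰ + 20×0.1×0.9¹⁹ = 0.12 + 0.27 = 0.39.

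The cost is SAP wording and a wide interval: the interaction has low power, so the slope difference should be read by its CI and a non-significant result should not be taken as no difference. Baseline TMG and ultrasound must be available in CON. The documents do not restrict them to EXP; without them Group×baseline CMJ can still be fitted.

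### In primary moderation (b), baseline error shifts the slope of ΔCMJ on baseline CMJ, and every simple slope, downwards, so none can be read against zero, although the interaction test itself is not biased

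*Combined protocol and SAP*

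**What the plan says.** The combined protocol and SAP defines the outcome under *Data handling and derived variables*: "ΔCMJ and percentage change (% ΔCMJ) will be computed relative to baseline". The same section treats jump height as error-prone: "At each time point, CMJ height is the mean of three trials", which I take to include baseline, and "Individual response is classified using MDC". It gives no value for the MDC, a standard error of measurement or an ICC.

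Under *Moderation and mediation (pre-specified)*, primary model (b) asks whether each of three baseline morphology measures (thickness, pennation angle and fascicle length) "modifies the effect of baseline CMJ on Δ CMJ". Model (a) asks whether "baseline CMJ modifies the effect of %MHC-I on Δ CMJ". Predictors and moderators are mean-centred and collinearity is checked. A significant interaction is followed by simple slopes at −1 SD, the mean and +1 SD, with bootstrap 95% CIs and plots.

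*Assumptions, multiplicity, and robustness* adds that moderation is meant for estimation and does not alter the primary inference.

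The plan does not say which arm or arms enter the moderation models. It specifies no Group × baseline CMJ term, no separate baseline reading for the predictor and no reliability correction.

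**The concern.** The focal predictor in (b) is also subtracted inside the outcome. An athlete who happens to jump below their usual height at baseline gets a lower predictor value and a larger ΔCMJ. One who happens to jump above it gets the reverse. This alone tilts the line downwards.

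Mean-centring only moves the origin, the VIF check concerns correlation among predictors, and the bootstrap puts an interval around the shifted value. None of them removes the tilt. Nor does a larger sample: the shift stays the same while the interval narrows around it.

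The stake is the answer to who responds, in a trial whose title is about responsiveness. A reader who sees a simple slope with a CI below zero would naturally conclude that weaker jumpers gain more, and that pattern is expected when all athletes gain equally.

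**Working it through.** The documents state no figure on this point, so there is none to reproduce.

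**Inputs.** From the documents: ΔCMJ is post minus baseline, and model (b) regresses ΔCMJ on baseline CMJ, morphology and their product. Assumed, because the documents give no value: reliability R of the three-trial mean, 0.80 to 0.98 with 0.90 to 0.95 as the working range; number of athletes; true between-athlete SD of 5 cm; correlation ρ between true jump height and morphology, 0 or 0.5.

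**Algebra.** Let baseline B = T + e0 and post = T + c + e1, with the same gain c for everyone and independent errors of equal variance. Then Δ = c + e1 − e0, and:

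- Cov(B, Δ) = −Var(e0), so slope = −Var(e0)/Var(B) = −(1 − R)
- corr(B, Δ) = −√((1 − R)/2)
- with morphology in the model, slope = −Var(e)/[Var(T)(1 − ρ²) + Var(e)]

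At R = 0.90, Var(T) = 25 and Var(e) = 25 × 0.10/0.90 = 2.78. The slope is −2.78/27.78 = −0.10 with ρ = 0, and −2.78/(18.75 + 2.78) = −0.129 with ρ = 0.5. At R = 0.95, Var(e) = 25 × 0.05/0.95 = 1.32, giving −1.32/26.32 = −0.05 and −1.32/(18.75 + 1.32) = −0.066.

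**Simulation of model (b)** with equal true gains, 4,000 data sets per setting. The last two columns give how often the baseline coefficient is significantly negative (nominal 2.5%), for ρ = 0 to ρ = 0.5.

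| R | Slope, ρ = 0 | Slope, ρ = 0.5 | corr(B, Δ) | n = 30 | n = 60 |
|---|---|---|---|---|---|
| 0.98 | −0.02 | −0.026 | −0.10 | 6.6–8.5% | 10.9–14.0% |
| 0.95 | −0.05 | −0.066 | −0.16 | 11.5–13.7% | 21.9–27.5% |
| 0.90 | −0.10 | −0.129 | −0.22 | 20.7–25.8% | 39.0–48.8% |
| 0.80 | −0.20 | −0.25 | −0.32 | 38.2–45.6% | 68.9–77.7% |

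With an error-free baseline (R = 1.0) the slope is 0 and the rate at n = 60 is 2.4–2.6%, so baseline error is the cause. Counted two-sided at 5%, for 15 to 40 athletes at one minute, the false-significance rate is 11–28% at R = 0.90 and 8–15% at R = 0.95.

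The simple slopes move together. At R = 0.90, n = 30, ρ = 0 they average −0.102 at −1 SD and −0.099 at +1 SD. The interaction coefficient stays centred on zero, with type I error of 4.4–5.7% across settings.

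**Comparison with CON.** The artefact depends only on baseline error, which comes before the intervention and so is expected to be the same in both randomised arms. In 20,000 data sets per setting (total n = 40 or 60, R = 0.80 to 0.98), the EXP minus CON slope averaged within 0.002 of zero, with type I error of 4.9–5.1%. Those runs had Group × baseline CMJ without morphology. The extension to the three-way term rests on the same argument and was not simulated.

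**The case against.** The strongest reply is that the plan does not test the slope at issue. What (b) tests is the interaction, and that test holds its level when relations are linear and error variance is constant. This stands: it would be wrong to infer that the moderation question as worded, or the EXP versus CON result, is biased.

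Second, simple slopes appear only after a significant interaction. With no true interaction, a significant interaction together with a significant baseline slope at one minute occurs in only about 1–2% of data sets, so the 8–28% rates apply to the baseline coefficient itself and not to this route. That also stands. However, when a true interaction exists the slopes will be shown and all are shifted, and the baseline coefficient is a term of the fitted model in any case.

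Third, the plan limits moderation to estimation. This protects the primary conclusion, but it does not help an estimate whose level is biased.

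Three stronger readings are not supported:

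- The slope is not negative in every sample. At R = 0.98 and n = 20 it was negative in only about 65–68% of runs, and a true positive relation steeper than (1 − R)/R (0.111 at R = 0.90, 0.053 at R = 0.95) would outweigh the shift.
- The documents nowhere say that weaker jumpers respond more. That is a foreseeable misreading, not a stated conclusion.
- Fitting the model at all five minutes would give a false slope at one or more of them in 26–61% of cases. That figure cannot be charged to the coupling: with the coupling removed the rate is already about 18–22% from five looks, and the plan does not say (b) is fitted minute by minute.

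**Conclusion.** The concern holds for the level of the slopes. In model (b), the baseline CMJ coefficient and each simple slope with its CI are shifted by about −(1 − R). For R of 0.90 to 0.95 that is −0.10 to −0.05 cm per cm, and somewhat more if morphology correlates with jump height. The baseline CMJ coefficient in model (a) has the same problem. The interaction test (given constant reliability across morphology) and the primary EXP versus CON inference are unaffected. The direction of the shift follows from the definitions and from any baseline error at all. Its size rests on R, which the documents do not give; at R = 0.98 it would be only −0.02.

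**What to change.** In *Moderation and mediation (pre-specified)*:

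1. State that both arms enter model (b). Add Group × baseline CMJ and Group × baseline CMJ × morphology.
2. Interpret EXP baseline slopes and simple slopes only as differences from the corresponding CON slopes, with CIs for those differences, and not against zero.
3. As a sensitivity check within EXP, use one baseline trial as predictor and the mean of the other two to form ΔCMJ. In simulation this gave 4.1–5.7% false positives. It removes only trial-level error: error shared by all baseline trials but not by later ones remains.
4. State, for models (a) and (b), that a negative baseline slope against zero is not evidence of differential response.

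The cost is SAP wording and a re-coded model on jumps already planned. The main downside is precision. With equal arms and equal residual variance, the variance of a slope difference is twice that of one arm's slope, so its standard error is about √2 = 1.41 times as large. The single-trial predictor in step 3 is also less reliable than a three-trial mean, so it weakens any true slope.
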